5.0	
 Section 8.12: Revised 12 month visit to 6 month visit (or after the 6 month visit due CIP v4 follow-up requirements); for subjects who exited early, recommended interval for follow-up for potential adverse events updated from 12 months to 6 months; sample size revised from 30 subjects to 15 subjects. 	[name], Senior Clinical Research Specialist [name], Principal Statistician

5.0	
 Section 12: Revised planned analyses; removed analysis to occur after completion of all 30 subject index procedures and 1 week follow-up visit, and modified the analysis to occur after completion of all subject follow-up visits through 12 months to occur after all subjects have completed follow-up visits through at least 6 months and have been exited from the study. 	[name], Senior Clinical Research Specialist [name], Principal Statistician
5.0	
 Section 12.1: Revised sample size to 15 subjects; removed "Assuming there are 30 ArcticLine cryoablation procedures in the study and the SAE rate is 3.3% (1/30 subjects: the rate of cryoablation procedure events in the STOP AF pivotal trial [PMA #P100010] was 3.1%), the exact 95% confidence interval will have a width of 17%". 	[name], Senior Clinical Research Specialist [name], Principal Statistician
5.0	
 Section 12.5: Replaced 12 month visit with 6 month visit in the endpoint definition; removed 12 month Holter; added a note that effectiveness data collected beyond the 6 month visit due to CIP Version 4 follow-up requirements will be adjudicated and included in the final report. 	[name], Senior Clinical Research Specialist [name], Principal Statistician
5.0	
 Section 12.6 and 12.8: Replaced 12 month visit with 6 month visit; added a note that safety data collected beyond the 6 month visit due to CIP Version 4 follow-up requirements will be adjudicated and included in the final report. 	[name], Senior Clinical Research Specialist [name], Principal Statistician
5.0	
 Grammatical and formatting updates throughout. 	[name], Senior Clinical Research Specialist [name], Principal Statistician

The purpose of the ArcticLine Feasibility study is to collect preliminary safety and effectiveness data on the ArcticLine Catheter when used to treat persistent Atrial Fibrillation (AF) and right atrial Cavotricuspid Isthmus (CTI) dependent atrial flutter (“typical atrial flutter”). These data will be used to guide subsequent product development activities for the ArcticLine Catheter, including feedback on device design and input into a future pivotal study.

The principal end of the Statistical Analysis Plan (SAP) for the ArcticLine Feasibility study is to provide pre-analysis documentation and rationale for the statistical procedures that will be used in the planned analyses performed throughout this investigation. Specifically, this plan outlines methods used in this study’s pre-planned interim safety report(s) and final report. It does not limit the analysis that will be completed, as further analysis beyond what is specified in this document may occur.

This SAP was developed based on version 5 of the ArcticLine Feasibility Study Clinical Investigation Plan (referred to as the CIP in this SAP), finalized on 08-JUL-2019. Excerpts from the annotated Case Report Form (CRF) document, which was last updated on 09-AUG-2018, are included in several places within this SAP.

4. Study Objectives

4.1 Primary Objective

Estimate the incidence of ArcticLine Catheter-related and ArcticLine cryoablation procedure-related Serious Adverse Events (SAEs) with an onset date within 7 days post-procedure.

Primary Endpoint

ArcticLine Catheter-related or ArcticLine cryoablation procedure-related SAEs, with an onset date within 7 days post-procedure (except as noted below), as adjudicated by the Clinical Events Committee (CEC), described as follows:

- Atrioesophageal fistula*
 - * Includes atrioesophageal fistula with an onset date at any time after the study cryoablation procedure and is adjudicated by the CEC as either ArcticLine Catheter-related or ArcticLine cryoablation procedure-related.
- Cardiac perforation/tamponade
- Cerebrovascular accident
- Death
- Esophageal injury
- Major bleeding

- Myocardial infarction
- Pericarditis
- Phrenic nerve injury (ongoing at hospital discharge)
- Transient ischemic attack
- Vagal nerve injury resulting in esophageal dysmotility or gastroparesis
- Vascular access complications

4.2 Ancillary Objectives

4.21 Ancillary Objective #1

Estimate the percentage of patients with acute treatment success of the ArcticLine Catheter at the left atrial roof and posterior wall in patients with demonstrated entrance block of all pulmonary veins and who underwent roof and posterior wall ablation with ArcticLine.

Ancillary Endpoint #1

Subjects must have confirmed block at the roof line and posterior wall line via periprocedural assessment of posterior wall isolation at the completion of the cryoablation procedure to be considered an acute treatment success.

4.22 Ancillary Objective #2

Estimate the percentage of patients with acute treatment success of the ArcticLine Catheter at the mitral isthmus in patients who underwent mitral isthmus ablation with ArcticLine.

Ancillary Endpoint #2

Subjects must have confirmed bi-directional conduction block at the mitral isthmus line via periprocedural assessment at the completion of the cryoablation procedure to be considered an acute treatment success.

4.23 Ancillary Objective #3

Estimate the percentage of patients with acute treatment success of the ArcticLine Catheter at the CTI in patients who underwent CTI ablation with ArcticLine.

Ancillary Endpoint #3

Subjects must have confirmed bi-directional conduction block at the CTI line via periprocedural assessment at the completion of the cryoablation procedure to be considered an acute treatment success.

4.24 Ancillary Objective #4

Characterize chronic treatment success of the ArcticLine Catheter in patients with demonstrated entrance block of all pulmonary veins.

Ancillary Endpoint #4

Chronic treatment success is the opposite of chronic treatment failure. Treatment failure is any of the following:

- AF/AFL/AT episodes of at least 30 seconds duration from the end of the 90 day blanking period through the 6 month visit.
- Per section 8.6.1 for the CIP, the initiation of a new Class I or III Antiarrhythmic Drug (AAD) after the 90 day blanking period, or a dose increase in an already prescribed Class I or III AAD after the 90-day blanking period. (Further details on treatment failures due to repeat ablations are specified in section 7.2.6.)
- Reablation for the treatment of recurrent AF/AT/AFL after the 90 day blanking period. (Further details on treatment failures due to repeat ablations are specified in section 7.2.6.)

4.25 Ancillary Objective #5

Estimate the incidence of ArcticLine Catheter-related and ArcticLine cryoablation procedure related serious adverse events (SAE) through the 6 month visit.

Ancillary Endpoint #5

ArcticLine Catheter-related or ArcticLine cryoablation procedure-related SAEs, as adjudicated by the Clinical Events Committee (CEC).

4.26 Ancillary Objective #6

Characterize procedural data:

- Total procedure time
- Total ArcticLine Catheter use time
- Left atrial dwell time
- Total fluoroscopy time
- Total fluoroscopy time during ArcticLine Catheter use
- Application duration

- Number of applications
- Fluoroscopy dose

Ancillary Endpoint #6

- Total procedure time is defined as time from first venous access to time of last catheter removal.
- Total ArcticLine Catheter use time is defined as cumulative time from each introduction of ArcticLine Catheter into the body to its removal.
- Left atrial dwell time is defined as time from transeptal puncture to time of removal of last sheath/catheter from the left atrium.
- Total fluoroscopy time is defined as total fluoroscopy time used during the procedure.
- Total fluoroscopy time during ArcticLine Catheter use is defined as the cumulative fluoroscopy time from each introduction of ArcticLine Catheter into the body to its removal.
- Application duration is defined as total duration in which cryoablation from the ArcticLine Catheter is applied to cardiac tissue overall and individually to each target area.
- Number of applications is defined as the total number of times in which the ArcticLine Catheter was used to ablate cardiac tissue overall and individually to each target area.
- Total fluoroscopy dose is defined as the amount of radiation deposited into the tissue, measured in Gy or mGy units.

4.27 Ancillary Objective #7

Estimate the incidence of adverse events (AEs) through the 6 month visit.

Ancillary Endpoint #7

Characterize adverse events through the 6 month visit, described as follows:

[figure not shown]
- Atrioesophageal fistula
- Cardiac perforation/tamponade
- Cerebrovascular accident
- Coronary artery spasm
- Death
- Esophageal injury
- Lung injury (including hemoptysis)
- Major bleeding
- Myocardial infarction
- Pericarditis
- Phrenic nerve injury (ongoing from hospital discharge)
- Pulmonary vein stenosis

- Symptomatic persistent iatrogenic atrial septal defect
- Transient ischemic attack
- Vagal nerve injury
- Vascular access complications

5. Investigation Plan

The purpose of the study is to collect preliminary safety and effectiveness data on the ArcticLine Catheter when used to treat persistent AF and right atrial CTI dependent AFL, or “typical atrial flutter”. These data will be used to guide subsequent product development activities for the ArcticLine Catheter, including feedback on device design and input into a future pivotal study.

Medtronic is sponsoring the ArcticLine Feasibility Study: a prospective, interventional, multicenter, non-randomized, single arm, unblinded clinical study. The study design diagram is shown in Figure 1. Up to 15 subjects will be enrolled in up to 4 centers in the United States and Canada, and will be treated with the ArcticLine Catheter.

6. Determination of Sample Size

The expected sample size is approximately 15 subjects, and is based on historical precedent for other feasibility studies, rather than a statistical derivation. The sample size of 15 treated subjects for this study was chosen with the goal to collect preliminary safety and effectiveness data on the ArcticLine

Catheter's use in both the left and right atrium. Assuming there are 15 ArcticLine cryoablation procedures in the study and the ArcticLine cryoablation procedure-related SAE rate is 6.7% (1/15 subjects: the rate of cryoablation procedure events in the STOP AF pivotal trial [PMA #P100010] was 3.1%), the exact 95% confidence interval will have a width of 32%.

7. Statistical Methods

7.1 Study Subjects

7.1.1 Disposition of Subjects

Subjects included in the primary analysis cohort require all of the following conditions: eligibility, consent to be studied, assessment for treatment of one or more pulmonary veins, and ablation with the ArcticLine Catheter. The study will collect data on subjects who consented to be studied and to the procedure, but who were given a different treatment at the time of operation (e.g. PVI only), but these cases will not affect the analysis of primary or ancillary objectives, as they do not meet the criteria of undergoing an ArcticLine ablation.

7.1.2 Clinical Investigation Plan (CIP) Deviations

Protocol deviations will be described using frequency tables and listings. As stated above in section 7.1.1, subjects will be excluded from analysis of primary or ancillary endpoints if any of these conditions apply:

- * Subject does not meet the study's entry criteria at the time of the procedure
- * Subject did not consent to the procedure
- * Subject did not undergo a procedure with the ArcticLine Catheter.

Handling of visit window and rhythm monitoring deviations as it affects the study's ancillary endpoint #4 is discussed further in section 7.2.6.

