12.1. Primary Objective

Estimate the incidence of ArcticLine Catheter-related and ArcticLine cryoablation procedure-related serious adverse events (SAEs) with an onset date within 7 days post-procedure.

Endpoint Definition

ArcticLine Catheter-related or ArcticLine cryoablation procedure-related SAEs, with an onset date within 7 days post-procedure (except as noted below), as adjudicated by the Clinical Events Committee (CEC), described as follows:

- Atrioesophageal fistula*
 - * Includes atrioesophageal fistula with an onset date at any time after the study cryoablation procedure and is adjudicated by the CEC as either ArcticLine Catheter-related or ArcticLine cryoablation procedure-related.
- Cardiac perforation/tamponade
- Cerebrovascular accident
- Death
- Esophageal injury
- Major bleeding
- Myocardial infarction
- Pericarditis
- Phrenic nerve injury (ongoing at hospital discharge)
- Transient ischemic attack
- Vagal nerve injury resulting in esophageal dysmotility or gastroparesis
- Vascular access complications

Sample Size

The sample size of 15 treated subjects for this study was chosen with the goal to collect preliminary safety and effectiveness data on the ArcticLine Catheter's use in both the left and right atrium.

Analysis Methods

The percentage of catheter related and cryoablation procedure related SAEs will be calculated as the number of procedures with at least one SAE meeting the endpoint definition divided by the number of cryoablation procedures. Each procedure will count, so subjects with repeat cryoablations will contribute more than once to the denominator. Exact methods will be used to construct a 95% confidence interval for the percentage of procedures with an SAE.

Determination of Patients for Analysis

All ArcticLine cryoablation procedures will be included. An ArcticLine cryoablation procedure is considered to have occurred once the ArcticLine Catheter is introduced into the vasculature.

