7.1.3 Analysis Sets

The '**Full Analysis Set**' consists of all enrolled and consented subjects. The Full Analysis Set will not be used for any pre-planned objectives; its principal use is in reporting adverse events that occur prior to the procedure. It can also be used in describing enrolled subjects who did not proceed to the index cryoablation procedure, if necessary, although no such analysis is currently planned.

The '**All Treated**' dataset is the subset of consented subjects meeting all inclusion and exclusion criteria at the time of the index ablation procedure who undergo a cryoablation procedure. It consists of subjects not treated with ArcticLine after the initial cryoablation assessment (the '**PVI Only**' subset) as well as subjects treated with the ArcticLine catheter. Subjects in the PVI only subset will be identified by

a response of 'Yes' to the question 'In the opinion of the investigator, is PVI only sufficient to treat the subject?' on the Administrative Information section of the PROCEDURE Case Report Form (CRF):

In the opinion of the Investigator, is PVI only sufficient to treat the subject

NO YES PVISUFF_FAMQVAL /NY /1

If Yes, explain

PVIYEXP_FAMQVAL

There are no pre-planned uses for the All Treated and PVI Only datasets, other than in description of subject disposition in interim, annual and final reports, and publications.

The '**ArcticLine Treated**' dataset consists of the subjects from the 'All Treated' dataset who have an ArcticLine catheter inserted into the vasculature. The ArcticLine Treated dataset will be the main analysis cohort for this study, used in the analysis of all primary and ancillary objectives.

Determination of whether an ArcticLine catheter was inserted into the vasculature will be made based on observing a completed value for "What was the time of ArcticLine catheter insertion" in the Procedure Times section of the PROCEDURE CRF:

Procedure Times

What was the time the subject entered electrophysiology room	SUBENTM_PRSTDTC HH:MM (24 hour clock)
What was the time of first venous access	FVACCTM_PRSTDTC HH:MM (24 hour clock)
What was the time of transeptal puncture	TRNSPTM_PRSTDTC HH:MM (24 hour clock)
What was the time of ArcticLine catheter insertion	ALCTITM_PRSTDTC HH:MM (24 hour clock)
What was the time of ArcticLine catheter removal	ALCTRTM_PRSTDTC HH:MM (24 hour clock)

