The use of exact (Clopper-Pearson) methods of describing the binomial rate of ArcticLine procedure-related SAE's, and the associated 95% confidence interval, requires the condition of independent events. This condition is not met if primary endpoint events are more likely (or less likely) to occur in subjects who have already experienced them at their index ablation, or if all second ablations are more (or less) prone to endpoint events relative to index ablations. It is assumed that (A) the expected rates of primary safety events will be what was observed in previous Medtronic cryoablation studies (<5%), (B) the expected rate of repeat ablations is <15%, and (C) N = 15 subjects. Under these conditions, the first test of the independence assumption will be to check for any observation of *even a single subject* with primary safety events resulting from both an index ablation and subsequent repeat ablation. Observing one or more such subjects is sufficiently unlikely under conditions of independence of events within subjects (see statistical appendix for details). The second test performed will be to show independence of primary event rates between index and repeat ablations with Fisher's exact test. Under conditions of independence, a Fisher's exact test of event rates between first and second ArcticLine ablations should show $p > 0.05$. If either the event rate is associated with repeat ablations, or the event rate is not independent within subject, primary safety events will not be pooled between index and repeat

ablations, and instead will be reported separately. This analysis will be omitted if there are no primary endpoint events resulting from repeat ArcticLine ablation procedures.

Determination of Subjects for Analysis

All ArcticLine cryoablation procedures will be included. An ArcticLine cryoablation procedure is considered to have occurred once the ArcticLine Catheter is introduced into the vasculature.

7.23 Ancillary Objective 1

Estimate the percentage of patients with acute treatment success of the ArcticLine Catheter at the left atrial roof and posterior wall in patients with demonstrated entrance block of all pulmonary veins and who underwent roof and posterior wall ablation with ArcticLine.

Ancillary Endpoint #1

Subjects must have confirmed block at the roof line and posterior wall line via periprocedural assessment of posterior wall isolation at the completion of the cryoablation procedure to be considered an acute treatment success.

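### SAP 7.1.1–7.1.3 restrict the primary safety analysis to eligible subjects, whereas Protocol 12.1 and SAP 7.2.2 count every procedure once the ArcticLine Catheter is in the vasculature

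*SAP*

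**What the plan says.** **Every exposure counts.** For the primary objective, SAP 7.2.2 states "All ArcticLine cryoablation procedures will be included", and Protocol 12.1 has the same rule. Protocol 12.1 fixes the moment of exposure: "An ArcticLine cryoablation procedure is considered to have occurred once the ArcticLine Catheter is introduced into the vasculature". SAP 7.2.2 repeats this. Neither section mentions eligibility.

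**Only eligible subjects count.** Three consecutive SAP sections say otherwise.

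- SAP 7.1.1: "Subjects included in the primary analysis cohort require all of the following conditions: eligibility, consent to be studied". The list of conditions ends with "and ablation with the ArcticLine Catheter".
- SAP 7.1.2: "subjects will be excluded from analysis of primary or ancillary endpoints if any of these conditions apply". The first condition is "Subject does not meet the study's entry criteria at the time of the procedure".
- SAP 7.1.3 defines All Treated as the "subset of consented subjects meeting all inclusion and exclusion criteria at the time of the index ablation procedure" who undergo cryoablation. ArcticLine Treated "consists of the subjects from the 'All Treated' dataset who have an ArcticLine catheter inserted into the vasculature", and it is the set used for all primary and ancillary objectives.

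**Related text.** The note to Protocol 7.4 expects that some exclusion criteria may be discovered only during the procedure, and gives unsuitable anatomy as an example; such a subject is exited at that point. Protocol 8.12 says that data up to a subject's exit will be analysed. SAP 7.8 lists both the changes made in version 3 and the components absent from the protocol's analysis plan. The eligibility filter is in neither list.

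**The concern.** The primary objective is the rate of catheter- and procedure-related SAEs in the first human use of the device. Such a rate should describe everyone exposed. An eligibility filter applied at the procedure allows a subject to leave both numerator and denominator after exposure, for a reason such as anatomy that may itself be linked to risk.

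A programmer who builds ArcticLine Treated from SAP 7.1.3 will apply the filter; one who follows SAP 7.2.2 or Protocol 12.1 will not. With 15 treated subjects, one such difference can change the headline result. SAP 7.2.2 also notes that all procedures were complete when version 3 was written. If the choice is left open until the final analysis, it could be made with outcomes already known.

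**Working it through.** **1. Inputs.** SAP section 6 gives 15 procedures, an assumed rate of 1/15 = 6.7% and an exact 95% interval 32% wide. SAP 7.2.2 specifies Clopper-Pearson intervals. The number of exposed subjects who failed entry criteria is not in the documents, so I take 1 as the main case and 0 to 2 as the range.

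**2. Formula.** For x events in n procedures, the lower limit is the 2.5% quantile of Beta(x, n − x + 1) and the upper limit is the 97.5% quantile of Beta(x + 1, n − x). For x = 0 the lower limit is 0 and the upper limit is 1 − 0.025^(1/n).

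**3. The plan's own figure.** For 1/15 the limits are 0.17% and 31.95%, a width of 31.8%, which rounds to the stated 32%. Wald (25.2%) and Wilson (28.6%) widths do not match, so the plan's figure is Clopper-Pearson and it reproduces.

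**4. The two rules compared, one exposed subject ineligible.**

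| Events | All exposed | Filter applied, excluded subject had an event | Filter applied, excluded subject had no event |
|---|---|---|---|
| 1 | 1/15 = 6.7% (0.2 to 31.9) | 0/14 = 0% (0 to 23.2) | 1/14 = 7.1% (0.2 to 33.9) |
| 2 | 2/15 = 13.3% (1.7 to 40.5) | 1/14 = 7.1% (0.2 to 33.9) | 2/14 = 14.3% (1.8 to 42.8) |

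As an example of the zero-event limit: 1 − 0.025^(1/14) = 0.232.

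**5. Shifts in percentage points.** With one event: 0 − 6.7 = −6.7, or 7.14 − 6.67 = +0.5. With two events: 7.14 − 13.33 = −6.2, or 14.29 − 13.33 = +1.0.

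**6. Range.** With none ineligible the rules agree. With two ineligible and one event overall, the result is 0/13 = 0% (0 to 24.7) if the event was in an excluded subject, and 1/13 = 7.7% (0.2 to 36.0) if it was not.

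**7. Does other text settle the conflict?** SAP 7.4 treats as missing a subject who exits before a contact at day 7 or later and has had no event by discharge. It concerns incomplete follow-up. It stops an early-exit subject with an event from being called missing, but it does not override the exclusion in SAP 7.1.2. Protocol 8.12 points the other way from 7.1.2 without naming the primary denominator. Neither resolves the question.

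**The case against.** The strongest counter-argument is that the conflict may have had no effect. SAP 7.7 reports a final cohort of 15, the protocol caps treated subjects at 15, and Protocol 5.1 says treated subjects are not replaced. If that 15 is the analysed cohort, nobody was removed. This is the only evidence on the point and it weighs against the 14-subject scenarios, but SAP 7.7 does not say whether the count was taken before or after the filter.

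Secondly, SAP 7.2.2 could be read inside the set defined in 7.1.3, as fixing only the unit of analysis and its start. That would remove the contradiction within the SAP but leave the SAP at odds with Protocol 12.1. Protocol section 12 does leave data-handling rules to the SAP, but an unlisted narrowing of the primary safety population goes beyond handling detail.

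Thirdly, the path to exclusion after exposure is narrow. In the sequence in Protocol 8.4.1, mapping precedes the decision to use ArcticLine, so left atrial tachycardia could be found before the catheter goes in. Unsuitable anatomy is the more plausible route, and nothing requires it to be found before introduction.

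Finally, this is an estimation study with no hypothesis test and no statistical stopping rule. Adverse events are adjudicated by the CEC, deviations are listed, and the intervals overlap heavily. All of that stands, and it confines the matter to the tabulated rate and its denominator. The requirement in SAP 7.1.1 for ablation rather than insertion is loose wording in one sentence and is not shown to exclude anyone.

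**Conclusion.** The concern holds. The current text gives incompatible populations for the primary safety endpoint, and the narrower one departs from Protocol 12.1 without being declared. Under the assumption of one ineligible subject among 15 exposed, the estimate falls by 6.7 points (one event) or 6.2 points (two events) if that subject had an event, and rises by 0.5 or 1.0 points if not. The downward case is the safety concern, and treating it as the likelier direction assumes that subjects found ineligible during the procedure carry higher risk. Whether any exposed subject was ineligible cannot be established from the documents. The conflict should be fixed before the final analysis. Confidence is high for the contradiction; its effect on the result is unknown.

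**What to change.** For the primary objective and Ancillary Objectives 5 and 7, define the safety set as all consented subjects with a recorded ArcticLine insertion time, regardless of eligibility deviations or whether a freeze was delivered. The consent condition is not written in Protocol 12.1 and should be stated openly.

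- Remove the eligibility condition from SAP 7.1.1–7.1.3 for these analyses, and make 7.1.1 refer to introduction of the catheter, not ablation with it.
- Reconcile this with Protocol 12.8, which starts the procedure for Objective 7 at skin puncture.
- Record the correction in SAP 7.8.
- Report how many subjects have an insertion time and how many of those failed entry criteria. Give the eligible-only result as a labelled sensitivity analysis.
- Reconcile the exit note in Protocol 7.4 with the follow-up and data-use text in Protocol 8.12 for subjects already exposed.

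The cost is SAP wording and a short protocol clarification. The insertion time is already on the procedure CRF, so no new data are needed.
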